13.2.2 Per Protocol analysis set

The per protocol analysis set (PP) will be a subset of ITT population without major protocol violations, where "major" is defined has having the potential to meaningfully affect outcome. Also excluded will be subjects who received treatment on fewer than 50% of days during which they were eligible for therapy delivery.

Only observed values will be used in the endpoint analyses for the PP. Thus, the primary endpoint will be analyzed only on those subjects with an observed primary endpoint. Similarly, a subject will be included in the analysis of a secondary endpoint only if she has an observed value on that endpoint.

13.2.3 One-month Responders

The one-month responder analysis set will be a subset of ITT of subjects who are classified responders at one month.

All endpoints will also be assessed for this cohort of subjects for qualitative comparisons to treatments utilizing a trial period prior to permanent implant.

Number	Revision / Date	Page
G02-CLP-0002_US	Rev. 08 / 27 July 2021	48 of 75

13.3 Treatment of Missing Data for Efficacy Analyses

Frequency of missing data and the reasons for the missing data will be presented in the final report. For ITT effectiveness endpoints, a multiple imputation procedure will be used to impute missing endpoint data. Any patients missing endpoint data due to "failure" will be considered as a failure for the effectiveness analysis. Further sensitivity analyses will include, but may not be limited to, a tipping-point analysis for handling missing data.

Baseline variables included in the multiple imputation procedure may consist of:

- Age
- Number of UUI episodes per day
- OAB duration
- Number of prior attempted OAB treatments

13.4 Sample Size Considerations

The sample size was calculated using PASS 2015 software by a one-sided exact test for a single binomial population, under the following assumptions:

- Significance level = 0.025 (one-sided)
- Power ≥ 90%
- Assumed treatment success rate = 65%
- Prespecified performance goal = 50%.

Given these assumptions, 134 evaluable subjects would be required to participate in the trial, taking into account an assumed attrition rate of 15%.

The total sample size for this trial, however, is driven by an important secondary objective:

To demonstrate the proportion of responders at 6 months post system activation, defined by ≥50% improvement in the average number of moderate-severe urgency episodes PPIUS degree 3,4 or <8 voids/day, is greater than 45%. A total of 89 evaluable subjects are required. Assuming 15% attrition rate, a total of 105 subjects meeting the criteria described above is needed. With 70% of enrolled subjects meeting the analysis criteria, 150 total sample size is sufficient to evaluate the secondary endpoint.

13.5 Statistical Analyses

13.5.1 Overview

Analysis of subject disposition and of safety will be done on the ITT population. The primary efficacy analysis and analyses of additional endpoints will be done on ITT. Supportive efficacy analyses will be done for the primary efficacy endpoint on the PP population and for other efficacy endpoints in both ITT and PP population.

Number	Revision / Date	Page
G02-CLP-0002_US	Rev. 08 / 27 July 2021	49 of 75

The data will be summarized in tables listing the mean, standard deviation median, minimum, maximum and number of subjects for continuous data, or in tables listing count and percentage for categorical data where appropriate. Descriptive statistics will be provided by time point both numerically and graphically as appropriate. Data listing by subject will be provided.

All statistical analyses will be performed, and data appendices will be created using the SAS® system. The effects of noncompliance, dropouts, and possible covariates such as Age will be assessed to determine the impact on the general applicability of results from this study.

13.5.2 Subject Disposition

Subject disposition will be tabulated; the number of enrolled, exposed, prematurely terminated and completed subjects will be summarized.

A list of dropouts will be prepared including reason for discontinuation, and time of discontinuation.

13.5.3 Safety

The safety analyses will be descriptive and narrative in nature, with AEs, including serious AEs (SAEs), coded and tabulated by body system, preferred term, group, severity and relation to device or procedure. Descriptive statistics and shift analysis tables will be provided as appropriate.

13.5.4 Primary Efficacy

For the primary analysis, the null hypothesis is that the response probability is less than or equal to 50%. We are interested in the alternative hypothesis that patients receiving the treatment have above 50% probability to achieve clinical improvement:

H₀: $\pi_{Renova} \le \pi_{PG}$ H₁: $\pi_{Renova} > \pi_{PG}$,

where π_{Renova} is the proportion of subjects meeting the pre-defined success criterion with RENOVA therapy (\geq 50% improvement in average number of urge related incontinence episodes), and π_{PG} is the prespecified performance goal (PG) of 50%.

Though sample size was conservatively calculated under an Exact Binomial test, the hypothesis testing will be conducted by constructing a two-sided, 95% Clopper-Pearson confidence interval. We will have succeeded in the trial if the lower bound of this confidence interval is above 50%.

13.5.5 Secondary Efficacy Endpoints

The following will be assessed as formal secondary efficacy endpoints:

 Proportion of subjects with ≥ 10 points (MID) improvement compared to baseline in HRQL (measured by the OAB-q) at 6 months post system activation

Number	Revision / Date	Page
G02-CLP-0002_US	Rev. 08 / 27 July 2021	50 of 75

- Proportion of responders at 12 months post system activation, defined as ≥ 50% improvement in either average number of urgency related incontinence episodes or average number of large (severe) urgency related incontinence episodes, as measured by 7-day Patient Voiding Diary.
- Proportion of responders at 6 months post system activation as demonstrated by ≥ 50% improvement in the average number of moderate-severe urgency episodes (PPIUS degree 3,4) or < 8 voids/day

Durability of effect will be based on 12-month follow-up data and all secondary efficacy endpoints will be analyzed in the three efficacy analysis sets—ITT, PP and OR1.

13.5.6 Additional Efficacy Endpoints

The following endpoints will be assessed as other endpoints for the 6-, 12-, 24- and 36-months post activation, without formal hypothesis testing and type I error control.

- Incidence of procedure or device related adverse events from 12- to 36-months post activation.
- Patient Global Impression of Improvement (PGI-I) score.
- Treatment Benefit, Satisfaction, and Willingness to Continue (BSW).
- Reduction in the average number of severe/large urgency related incontinence episodes.
- Improvement in OAB-q (HRQL and symptoms severity) at 6- and 12- months post system activation.
- Changes in the following OAB symptoms as measured by voiding diary compared to baseline:
 - Reduction in the number of micturition episodes.
 - Reduction in the number of urgency related incontinence episodes.
 - Reduction in degree of urgency prior to void on Patient Perception of Intensity of Urgency Scale (PPIUS) from 0-4.
 - Reduction in severity of incontinence episodes (amount leaked).
- Proportion of dry subjects following treatment with the RENOVA iStim System as measured by 3
 consecutive days of a patient voiding diary.
- Assessment of fecal incontinence symptoms in patients suffering from mixed fecal and urine incontinence.
- Patient compliance with treatment.
- Duration from treatment initiation to symptoms improvement (in subset of patients who stopped treatment after completing the 12 month visit and started again when consented for the long term follow-up
- Assessment of treatment regimen

Number	Revision / Date	Page
G02-CLP-0002_US	Rev. 08 / 27 July 2021	51 of 75

Device usage

All additional efficacy endpoints will be analyzed in all three efficacy analysis sets—ITT, PP and OR1.

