11.4.6 BlueWind RENOVA iStim™ System Long-Term Follow Up (LTF) Visits – Visits 9-12

Long term follow-up visits will be performed at 18, 24, 30, 36-months post activation.

If a subject already completed the 12-months follow-up and exited the study, she will be invited for a Long-Term Follow-Up Consent Visit in which, following her consent to participate in the long-term follow-up study, some eligibility criteria will be verified and treatment parameters setting will be performed. Subjects will enter the visit schedule using their original system activation date. Any visit that has already passed will not be counted as a missed visit.

If the subject discontinued treating herself when she exited the study and is activated again she will be asked to treat herself for 30 minutes, twice a day, for at least 4 weeks prior to completing the first LTF visit. During this period, she will be asked to complete a modified daily diary to capture incontinence episodes, time to treatment effect, and symptom improvement questions.

Subjects continuing to the long-term follow-up will be asked to treat themselves per physician discretion but not less than two 30-minute treatment per week.

All follow-up visits will require completion of 3-day voiding diary by the patient before coming to visit.

Follow-up visits 10 (24-months) and 12 (36-months) will be performed in clinic and will be similar to the 6 and 12-months follow-up visits

Follow-up visits 9 and 11 will be performed over a phone call unless the treatment is not effective enough or treatment parameters are not optimal or patient is experiencing an AE or device malfunction. In such cases the patient will arrive to the clinic and a visit similar to the 1, 3, and 9- months post activation will be performed.

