38.	Voiding Diary (UUI for ~4 weeks) *only for applicable subjects	X*				
39.	Usability/patient satisfaction questions		Х		Х	
40.	Parameter Setting †if in clinic		Χ [†]	Х	Χ [†]	х
41.	Leg circumference measurements	Х				
42.	Patient Training on wearable unit	X				
43.	Adverse Event	X	Х	Х	Х	Х
44.	Study completion/discontinuation form					Х

Number	Version / Date	Page
G02-CLP-0002 US	Rev. 08 / 27July 2021	66 of 75

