Any subjects enrolled prior to the COVID-19 outbreak may be subject to telephone follow-ups instead of onsite follow-up visits for a period of time. Interactions with affected subjects, then, would be different than for those who are routinely followed in the clinic, and only a subset of data will be able to be collected. A covariate adjusted logistic regression model, as described above, will be fit to assess the potential impact of COVID-19 on study outcomes, with an indicator variable indicating subjects enrolled prior to, and after, stay- at-home policies were enacted.

Finally, a test of homogeneity of effect across investigational center will be conducted. Descriptive statistics (e.g. success rate) will be reported for every participating center. Any center enrolling fewer than five subjects will be excluded from the formal test of homogeneity. To acknowledge that this test of homogeneity is fundamentally underpowered, a significance level of 0.15 will be used to determine whether a potential differential effect across centers exists and to trigger additional, exploratory analysis to better understand the nature of the difference.

13 Long-Term Follow-Up

Upon completion of the 12-month follow-up visits, patients will enter a long-term follow-up phase. Formal study visits will occur at 24 and 36 months. Less comprehensive visits conducted via telephone will be conducted at months 18 and 30. The telephone visits will assess adverse events and subject diary data.

Document ID	Revision / Date	Page
G02-CLP-0009	Rev. 06 / 18 May 2022	24 of 26

All primary, secondary and additional efficacy measures will be summarized using appropriate descriptive statistics - mean, median, standard deviation and 95% confidence intervals for continuous measures and frequency distributions for categorical or binary data. Adverse events, and treatment regimen data will be summarized.

14 Data Listings

Data listings will be provided for all data available from the CRF.

15 Computer Software

All statistical analyses will be carried out using SAS® Version 9.4 or higher under Windows® 2016 Terminal.

Document ID	Revision / Date	Page
G02-CLP-0009	Rev. 06 / 18 May 2022	25 of 26

16 Appendix 1: Rules for Correction of Discrepancies in Paper Diaries

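### Time from restarting treatment to improvement: a woman who does not improve has no duration and the plan has no rule for her, so the generic summaries would describe improvers only

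*Protocol*

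**What the plan says.** The endpoint appears in the protocol synopsis, in 10.3.3 and in 13.5.6: "Duration from treatment initiation to symptoms improvement (in subset of patients who stopped treatment after completing the 12 month visit" and began again on consenting to long-term follow-up. It carries no formal test.

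The data source is in protocol 11.4.6. A woman who had stopped is asked to "treat herself for 30 minutes, twice a day, for at least 4 weeks prior to completing the first LTF visit", and meanwhile to "complete a modified daily diary to capture incontinence episodes, time to treatment effect, and symptom improvement questions". The long-term schedule (protocol section 26) shows this diary as "Voiding Diary (UUI for ~4 weeks) *only for applicable subjects". The diaries at the long-term visits themselves cover only 3 days.

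On analysis, protocol 13.5.1 says: "The data will be summarized in tables listing the mean, standard deviation median, minimum, maximum and number of subjects for continuous data". SAP 13 covers long-term efficacy measures with "mean, median, standard deviation and 95% confidence intervals for continuous measures" and frequency distributions for categorical or binary data. SAP 7.1 excludes the additional endpoints from multiple imputation. The SAP lists of additional endpoints (8.4 and 12.6.3) do not contain this one. Neither document defines improvement for it, gives a censoring rule, or names a time-to-event summary.

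**The concern.** The endpoint is a time to an event, watched through a window of limited length. A woman whose symptoms have not improved when her diary ends contributes no duration, although she does carry information: her time to improvement is longer than her diary. A later 3-day diary might show that she has since improved, but it could not date the change.

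The summaries available in the plan are those for an ordinary continuous variable. Computed over the durations that were recorded, they answer how fast onset was among women who improved during the diary. The result is likely to be read as the answer to a different question: how soon a woman who restarts can expect benefit. The two agree only if every restarter improves within the diary. Otherwise the reported figure is too short, and it changes little as the share who improve falls.

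**Working it through.** **No plan figure to reproduce.** The documents give no subset size, expected onset time or share of restarters expected to improve. What follows shows the direction of the bias and illustrates its size under stated assumptions.

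**Direction.** Let T be the time from restart to improvement and C the end of the diary. T is recorded only when T ≤ C. A mean or median of recorded values is therefore conditional on T ≤ C. The women left out all have T > C, so including them can only lengthen the result.

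**Inputs.**
- C = 28 days, from the 4 weeks in protocol 11.4.6 and section 26 (4 × 7).
- p = share improving by day 28. Not in the documents; assumed 90% down to 30%.
- Shape of onset. Not in the documents; assumed exponential, then uniform as a check.

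**Exponential onset.** Rate λ = −ln(1 − p)/28.
- Median, all restarters: ln 2/λ
- Median, improvers only: −ln(1 − p/2)/λ
- Mean, improvers only: 1/λ − 28(1 − p)/p
- Mean restricted to 28 days, all restarters: p/λ

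Worked for p = 0.70:
- λ = 1.2040/28 = 0.0430 per day
- median, all restarters: 0.6931/0.0430 = 16.1 days
- median, improvers only: 0.4308/0.0430 = 10.0 days
- mean, improvers only: 23.3 − 12.0 = 11.3 days
- restricted mean, all restarters: 0.70 × 23.3 = 16.3 days

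| Share improving by day 28 | Median, improvers only | Median, all restarters | Mean, improvers only | 28-day restricted mean, all |
|---|---|---|---|---|
| 90% | 7.3 | 8.4 | 9.0 | 10.9 |
| 70% | 10.0 | 16.1 | 11.3 | 16.3 |
| 50% | 11.6 | 28.0 | 12.4 | 20.2 |
| 30% | 12.8 | not reached by day 28 | 13.2 | 23.6 |

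The gap in medians is 8.4 − 7.3 = 1.1 days at 90%, 16.1 − 10.0 = 6.1 days at 70%, and 28.0 − 11.6 = 16.4 days at 50%. Below 50% the all-restarter median lies beyond the diary, yet the improver-only median still reads about 12 to 13 days.

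**Uniform onset over the 28 days among improvers.** The improver-only median is 14 days whatever p is. Over all restarters it is 14/p: 15.6 days at 90%, 20.0 at 70%, 28.0 at 50%, and not reached below that. The direction is the same.

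**Boundary case.** If every restarter improves within the diary, the two groups coincide and there is no bias.

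**The case against.** The strongest reply is that the plan does not prescribe this analysis. No sentence says that women who do not improve are dropped, and both documents leave room by calling for descriptive statistics that are appropriate to the data. That stands. The exclusion is implied: it is where generic summaries lead when there is neither imputation nor a censoring rule. A reader might infer that the sponsor chose a biased method; the documents show only that none was specified.

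Protocol 13.5.1 also requires the number of subjects beside the summary. That is a partial safeguard. A reader who also knew how many women restarted could see how many had no recorded duration, but the median itself would not be corrected.

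A reader might put the non-improving share at 35% (from the 65% assumed response in protocol 13.4) or 49% (from the 51% in protocol section 8). The documents do not support that transfer. Both figures concern a 50% reduction in leaking episodes, the first as a 6-month assumption for all implanted women and the second from the earlier trial of the first-generation device. Here improvement is undefined and is captured partly by symptom questions, so it could be much more common. The women are also selected: they completed 12 months, still have the implant, consented again and restarted.

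Nor is 28 days a firm ceiling on a recorded duration. Protocol 11.4.6 makes 4 weeks a minimum before the first long-term visit, and only the schedule says about 4 weeks. Diary lengths may therefore differ between women, which is a further reason to use a method that allows unequal follow-up.

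**Conclusion.** The point holds as a gap in the analysis plan with a known direction. The endpoint is missing from the SAP, improvement is undefined, and the only applicable summaries, taken over recorded durations, would make onset look faster than it is among all women who restart, unless all of them improve within the diary.

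The size is not computable from the documents, since neither the share improving nor the subset size is given. The figures above rest on an assumed onset shape and a 28-day diary. On those assumptions the understatement of the median is about 1 day if 90% improve and about 6 days if 70% do; below 50% no all-restarter median is observed at all.

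The consequence is small. This is one descriptive endpoint in a subset, and it has no bearing on the primary or secondary tests.

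**What to change.** - Add the endpoint to SAP 8.4, 12.6.3 and 13.
- Define the improvement event and its reference level from the modified daily diary; Kaplan-Meier cannot be run without a defined event. SAP Appendix 2, still to be completed before database lock, could hold the derivation.
- Analyse all women who restart by Kaplan-Meier from the restart date, censoring those not improved at their last diary day.
- Report the number restarting, the proportion improved by day 28 with a 95% CI, and the median over all restarters, or 'not reached'.

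The cost is a few lines of SAP text and one table, from a diary that is already planned. The reported onset may look slower than a summary of improvers alone.

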13.5.7 Covariate Analyses

Covariate analyses will be done by comparing each endpoint between groups defined by the levels of the covariate at baseline, where continuous variables will be coded into two levels by median split. Analyses will be done by logistic regression. Covariates will include, but are not limited to:

- Age
- BMI
- OAB duration at baseline

Additionally, formal subgroup analyses will be conducted to assess the effects on the primary endpoint of antidepressant medications, and also to assess the potential impact of COVID-19 on the study outcomes. Details of these analyses are outlined in the SAP.

Finally, a test of homogeneity of effect across investigational center will be conducted. Descriptive statistics (e.g. success rate) will be reported for every participating center. Any center enrolling fewer than five subjects will be excluded from the formal test of homogeneity. To acknowledge that this test of homogeneity is fundamentally underpowered, a significance level of 0.15 will be used to determine whether a potential differential effect across centers exists and to trigger additional, exploratory analysis to better understand the nature of the difference.

13.5.8 Interim Analysis

An administrative interim analysis is will be performed at the time one-month post activation data is available on 50 implanted subjects. This analysis is intended to support necessary company financing activities, and visibility of the results will be restricted to only those involved in those activities. Importantly, no person – BlueWind employee or consultant – who has interaction with investigational sites will have visibility to interim results. The interim analysis does not require subsequent adjustment of the overall trial significance level (0.025) to account for type I error inflation because:

- it is administrative in nature only, with limited distribution of the results
- it is looking primarily at 1-month data, which may not be reflective of the primary endpoint at 6 months
- the interim analysis is at the time 1/4 to 1/3 of the total number of enrolled subjects is 1/6 of way (1 month follow-up) toward the primary effectiveness endpoint (at 6 months follow-up). This represents 1/18th to 1/24th of the total trial information. Under an O'Brien-Fleming alpha spending function, virtually zero alpha would be allocated to the interim analysis
- there is no opportunity to terminate the trial early for effectiveness.

Number	Revision / Date	Page
G02-CLP-0002_US	Rev. 08 / 27 July 2021	52 of 75

Only data from the first 50 subjects with one-month post activation data will be reviewed. Data from enrolled subjects that do not yet have 1-month data available will be excluded from the analysis. All data from the 50 subjects will be included in the review (i.e. data from follow-up visits subsequent to the 1-month visit will also be summarized, if available).

The analysis will involve, in summary form, results on:

- Device and procedure-related adverse events
- Percent improvement in the average number of urgency-related incontinence episodes, as compared to baseline.
- Proportion of subjects with ≥10 points (MID) improvement compared to baseline in HRQL (based on OAB-q) at each follow-up post system activation
- Proportion of responders at each follow-up visit post system activation, as demonstrated by ≥50% improvement in the average number of moderate-severe urgency episodes PPIUS degree 3,4 or <8 voids/day

Other data summaries, such as questionnaires (e.g., PGI-I, BSW), demographics, the proportion of dry subjects, and outcomes of interest may also be summarized

14. Data Management

Data management services will be provided by TechnoSTAT Ltd. Electronic Data Capture and adverse events coding will be performed by Axiom Real-Time Metrics. It is the responsibility of the study sponsor to ensure that the investigation is conducted and the data is generated, documented (recorded), and reported in compliance to the investigational plan and study agreements, adherence to regulations, and accuracy of study data.

